7.1.2 Weekly Visits During RT

During regular visits with medical staff, study subjects will also meet with study staff. Study staff will obtain photographs of the area of irradiation. Study staff will obtain photographs of the area of irradiation. Study personnel will collect the skin toxicity assessment (Appendix H). Any adverse events will be noted and addressed. Subjects will complete the Dermatology Life Quality Index (Appendix I). Study personnel will provide KeraStat Cream, as needed, to subjects randomized to receive KeraStat Cream. Subjects randomized to standard of care will follow the instructions of their radiation oncologist.

7.1.3 Post-Radiation Therapy Visit

During a final follow up visit with medical staff (estimated at 4 to 6 weeks post radiation therapy termination), or if the subject terminates the study, the study subject will meet with study staff. Study staff will obtain photographs of the area of irradiation. Study personnel will collect the skin toxicity assessment (Appendix H). Any adverse events will be noted and addressed. Subjects will complete the Dermatology Life Quality Index (Appendix I).

7.2 Study Calendar

	Prior to RT Start	Weekly During RT ^a	1-month Follow- up Visit
Informed consent	Χ		
Demographics (Appendix B, C, D)	X		
Medical history (Appendix E)	X		
Medications (Appendix F)	Χ		
Compliance & Tolerability Assessment (Appendix G)	Х	Х	Х
Toxicity Assessment Form (Appendix H)	Х	X	Х
Dermatology Life Quality Index (Appendix I)	Х	X	Х
Photographic Documentation of the Skin in the Region of Interest	Х	Х	Х

^a Assessments may occur within +/- 5 days of weekly on-treatment visit. On-treatment visits occur weekly until patient has completed (or stopped) treatment. If treatment breaks are necessary, patient may be seen on weeks 8 or 9 if needed.

8.0 Adverse Events List and Reporting Requirements

8.1 Adverse Event Definitions

8.1.1 Adverse Event (AE)

An adverse event (AE) is defined as any unfavorable or unintended dermatological condition.

8.1.2 Serious Adverse Event (SAE)

A serious adverse event (SAE) is any untoward medical occurrence that occurs irrespective of study treatment assignment, if it satisfies any of these criteria: results in death; is life-threatening; requires inpatient hospitalization or prolongs existing hospitalization; results in persistent or significant disability or incapacity or substantial disruption of the ability to conduct normal life functions; or if the event results in a congenital anomaly or birth defect.

8.1.3 Adverse Event Reporting

Subjects will be encouraged to spontaneously report any changes in baseline health from the time the subject enters the study through study completion.

^b Post-treatment assessments may occur within +/- 2 weeks of scheduled time point

Study staff also will inquire about AEs on each visit while the subject is in the research center.

8.1.4 Assessment of Causality

The Investigator is obligated to assess the relationship between study device and the occurrence of each AE/SAE. The Investigator will use clinical judgment to determine the relationship. Alternative causes, such as natural history of the underlying diseases, concomitant therapy, other risk factors, and the temporal relationship of the event to the study device will be considered and investigated.

The Investigator will assess causality based on the following definitions:

- Not Related (the AE was more likely explained by causes other than the study treatment).
- Related (the study treatment and AE were closely related in time and the AE
 may be explained by exposure to study product: e.g., known adverse effect or
 recurrence on re-challenge).

8.2 Recording Adverse Events

When an AE occurs, it is the responsibility of the Investigator to review all documentation (e.g., medical progress notes, laboratory, and diagnostics reports) relative to the event. The Investigator will then record all relevant information regarding an AE in the CRF.

The Investigator will attempt to establish a diagnosis of the AE based on signs, symptoms, and/or other clinical information. In such cases, the diagnosis should be documented as the AE/SAE and not the individual signs/symptoms.

8.2.1 Eliciting Adverse Event Reports

At each visit, subjects will be asked about AEs by means of a non-leading question, such as "how have you been since your last visit?" or "how has the treatment been?" In this way, possibly milder, but clinically important, side effects of the study device can be detected. SAEs will be reported promptly to KeraNetics as described in the following table once the Investigator determines that the event meets the protocol definition of a SAE.

8.3 Adverse Event Characteristics

CTCAE term (AE description) and grade: The descriptions and grading scales found in the revised NCI Common Terminology Criteria for Adverse Events (CTCAE) version 4.0 will be utilized for AE reporting. All appropriate treatment areas should have access to a copy of the CTCAE version 5.0. A copy of the CTCAE version 5.0 can be downloaded from the CTEP web site (http://ctep.cancer.gov).

- 'Expectedness': AEs can be 'Unexpected' or 'Expected' (see Section 7.1 above) for expedited reporting purposes only.
- Attribution of the AE:
- Definite The AE is clearly related to the study treatment.
- Probable The AE is likely related to the study treatment.
- Possible The AE may be related to the study treatment.
- Unlikely The AE is doubtfully related to the study treatment.
- Unrelated The AE is clearly NOT related to the study treatment.

8.4 STRC SAE Reporting Requirements

The Data Safety Monitoring Committee (DSMC) is responsible for reviewing SAEs for WFBCCC Institutional studies as outlined in Appendix K. All Adverse Events that occur during protocol intervention and are coded as either 1) unexpected grade 4, 2) unplanned inpatient hospitalization ≥ 24 hours (regardless of grade), or grade 5 (death) must be reported to the DSMC using the using the SAE console in WISER.

All WFBCCC Clinical Protocol and Data Management (CPDM) staff members assisting a Principal Investigator in investigating, documenting and reporting an SAE qualifying for DSMC reporting are responsible for informing a clinical member of the DSMC as well as the entire committee via the email notification procedure of the occurrence of an SAE.

8.5 WFUHS IRB AE Reporting Requirements

Any unanticipated problems involving risks to subjects or others and adverse events shall be promptly reported to the IRB, according to institutional policy. Reporting to the IRB is required regardless of the funding source, study sponsor, or whether the event involves an investigational or marketed drug, biologic or device. Reportable events are not limited to physical injury, but include psychological, economic and social harm. Reportable events may arise as a result of drugs, biological agents, devices, procedures or other interventions, or as a result of questionnaires, surveys, observations or other interactions with research subjects.

All members of the research team are responsible for the appropriate reporting to the IRB and other applicable parties of unanticipated problems involving risk to subjects or others. The Principal Investigator, however, is ultimately responsible for ensuring the prompt reporting of unanticipated problems involving risk to subjects or others to the IRB. The Principal Investigator is also responsible for ensuring that all reported unanticipated risks to subjects and others which they receive are reviewed to determine whether the report represents a change in the risks and/or benefits to study participants, and whether any changes in the informed consent, protocol or other study-related documents are required.

Any unanticipated problems involving risks to subjects or others occurring at a site where the study has been approved by the WFUHS IRB (internal events) must be reported to the WFUHS IRB within 7 calendar days of the investigator or other members of the study team becoming aware of the event.

Any unanticipated problems involving risks to subjects or others occurring at another site conducting the same study that has been approved by the WFUHS IRB (external events) must be reported to the WFUHS IRB within 7 calendar days of the investigator or other members of the study team becoming aware of the event.

Any event, incident, experience, or outcome that alters the risk versus potential benefit of the research and as a result warrants a substantive change in the research protocol or informed consent process/document in order to insure the safety, rights or welfare of research subjects.

9. STUDY DEVICE MATERIALS AND MANAGEMENT

9.1 Study Device

KeraStat Cream is a non-sterile, non-implantable, emollient-based wound dressing intended to act as a protective covering in the management of a variety of skin conditions. KeraStat Cream is designed to be topically applied to the skin surface. When applied, KeraStat Cream covers the skin or wound, isolating it from the external environment, absorbing excess exudate and facilitating a moist wound environment.

9.2 Study Device Packaging and Labeling

KeraStat Cream will be provided in multiuse tubes. The study device supplies will be maintained at the site under controlled conditions and dispensed by qualified personnel at the study site. The study device labels will contain information to meet the applicable regulatory requirements.

9.3 Study Device Storage

The study device must be stored at room temperature (15 to 30°C [59-86°F]). The study device must be dispensed or administered according to procedures described herein. Only subjects enrolled in the study may receive the study device, in accordance with all applicable regulatory requirements. Only authorized site staff may supply the study device.

9.4 Study Device Preparation

KeraStat Cream final product will be manufactured within applicable current Good Manufacturing Practice (cGMP) regulations in accordance with KeraNetics quality system. The product will be supplied in the form of a cream and packaged in a multi-use tube as detailed in Section 9.2.

9.5 Administration

KeraStat Skin Cream has been shown to moisturize the skin and reduce dryness, redness, and the appearance of inflammation. It should be applied as **needed** but **at least twice daily**.

In this study, patients will apply the cream at least twice-daily during the radiation treatments, 7 days per week.

9.6 Study Device Accountability

The Investigator is responsible for the study device accountability and record maintenance.

9.7 Study Device Handling and Disposal

Unused supplies, including the study device, will be disposed of using appropriate documentation according to International Conference on Harmonization-Good Clinical Practice (ICH-GCP), local requirements, applicable Occupational Safety and Health Administration (OSHA) and Environmental Protection Agency (EPA) regulations, and applicable study-specific procedures.

10.0 Data Management

Informed consent document	WISER
Protocol registration form	WISER
Appendix C	REDCap
Appendix D	REDCap
Appendix E	REDCap
Appendix F	REDCap
Appendix G	REDCap
Appendix H	REDCap
Appendix I	REDCap
Photographic Documentation of Skin in the	REDCap
Region of Interest	

11.0 Statistical Considerations

11.1 Analysis of Primary Objective

The completion rate will be used as a measure of feasibility, with participants with an average of 10 or more applications per week being classified as compliant. In each arm, a 95% confidence interval will be calculated around the estimate of compliance.

11.2 Analysis of Secondary Objective

- 11.2.1 The rate of discontinuation for any reason will be used as a measure of tolerability, with patients who do not discontinue the skin care regimen being classified as tolerant. In each arm, a 95% confidence interval will be calculated around the estimate of tolerability.
- 11.2.2 Proportion of EASR (CTCAE v5.0 Grade 2+ radiation dermatitis) will be compared between the KeraStat group and the RSC group at the end of treatment, using a Fisher's exact test.
- 11.2.3 Mean scores of the modified PRO-CTCAE patient-reported outcome scales collected each week over the 6-7 weeks of radiation therapy and at the onemonth post treatment follow-up visit will be compared between the KeraStat and RSC groups using a simple repeated measures analysis of variance model with treatment group as the independent variable of interest.
- 11.2.4 Mean DLQI score at each time point will be compared between the KeraStat and RSC groups, again using a simple repeated measures analysis of variance model with treatment group as the key independent variable. Additionally, the mean of the highest DLQI score across all time points will be compared between the KeraStat and RSC groups using a t-test.
- 11.2.5 Skin coverage (calculated as number of tubes of KeraStat Cream used per week) will be summarized with a frequency distribution and computation of central tendency and variability (mean, median, and standard deviation).

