2.1 Primary Objective(s)

To determine the feasibility of the use of KeraStat Cream in patients receiving radiotherapy for head and neck cancer.

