2.2 Secondary Objective(s)

- 2.2.1 To determine the tolerability of KeraStat Cream in patients receiving radiotherapy for head and neck cancer compared to routine skin care.
- 2.2.2 To assess the effectiveness of KeraStat Cream in reducing the severity of EASR in patients receiving radiotherapy for head and neck cancer, compared to routine skin care. This will be performed by evaluating:
 - 2.2.2.1 Objective evaluation of EASR using the CTCAE Version 5.0 scale of radiation dermatitis,
 - 2.2.2.2 Patient-reported outcomes of radiation dermatitis using the PRO-CTCAE version 1.0, and
 - 2.2.2.3 Dermatologic-specific quality of life assessment
- 2.2.3 To estimate the amount of KeraStat Cream used per patient and coverage on the skin.

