5.2 Secondary Outcomes

5.2.1 Tolerability is measured by the number of patients who discontinue skin care regimen due to intolerance for any reason.

^{*}Protocol Registration is open from 8:30 AM - 4:00 PM, Monday-Friday.

- 5.2.2 The effectiveness of KeraStat Cream in reducing EASR will be assessed as follows:
 - 5.2.2.1 Objective assessment of EASR, defined as Grade 2+ using the CTCAE version 5.0 scale of radiation dermatitis (Appendix H)
 - 5.2.2.2 Patient-reported assessment of skin toxicity using the PRO-CTCAE version 1.0 scale of radiation skin reaction (Appendix H)
 - 5.2.2.3 Dermatologic-specific quality of life will be measured using the Dermatology Life Quality Index (Appendix I)
- 5.2.3 Skin coverage by the will be calculated the number of tubes of KeraStat Cream used.

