Appendix M – 30 Day Treatment Follow-up Form

Study Number:	PID:
PI:	Date (mm/dd/yy): ///
Instructions: Fill out this form post was	shout to assess Adverse Events
Name of person completing form	
Did the subject have any adverse e SAE occurs in this period, report the Yes No	vents? If yes, document on AE log (Note*: If a event as required per protocol)
Was the subject removed from the s ☐ Yes ☐ No	study? If yes, document on off study form
Did the subject withdraw from the st ☐ Yes ☐ No	tudy? If yes, document on the off treatment form
Did the subject complete the study? ☐ Yes ☐ No	If yes, document on the off study form
Comment:	

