Appendix N – Off-Study Form

Study Number:	PID:
PI:	Date (mm/dd/yy):///
Instructions:	
Off Study:	
Off Study Date://	
Off Study Reason: Adverse Event/Side Effects/Comparison Death (if death fill out Survivation Decision Enrolling Physician Decision Patient lost to follow-up; Date Patient refused follow-up Protocol-defined follow-up composition Other Explain:	e of last contact (mm/dd/yy)://

WFBCCC 97319

Off Treatment Form

Study Number: PID:	
	dd/yy): //
Instructions: Off Treatment: 1. Off Treatment Date:/_/	
2. Off Treatment Reason: Adverse Event/Side Effects/Complication Alternative Therapy Cytogenetic resistance Death on Study Disease progression before active treatm Disease progression, relapse before active Enrolling Physician Decision Lost to follow-up No treatment, per protocol criteria Patient off treatment for other complicatine Patient withdrawal or refusal after beginn Patient withdrawal or refusal prior to beging Treatment completed per protocol criteriae Other	nent ve treatment ng disease ing protocol therapy inning protocol therapy
3. Explain:	

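### Tolerability is defined as stopping because of intolerance (5.2.1) but analysed as stopping for any cause (11.2.1), and the comparative objective 2.2.1 has no between-arm estimate

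*Combined protocol and SAP*

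**What the plan says.** Objective 2.2.1 is comparative: "To determine the tolerability of KeraStat Cream in patients receiving radiotherapy for head and neck cancer compared to routine skin care". The outcome that serves it, in Section 5.2.1, is: "Tolerability is measured by the number of patients who discontinue skin care regimen due to intolerance for any reason".

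The analysis in Section 11.2.1 begins: "The rate of discontinuation for any reason will be used as a measure of tolerability". Patients who do not discontinue the regimen are the tolerant ones, so every discontinuer counts as not tolerant. The only inference planned is: "In each arm, a 95% confidence interval will be calculated around the estimate of tolerability".

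Reasons for stopping are collected. Appendix G asks whether the assigned cream was discontinued in the past week and why. Section 6.6 requires the reason for withdrawal from the study to be recorded in the source documents and CRF. For a patient who withdrew, Appendix M says: "If yes, document on the off treatment form". That form has a category "Off Treatment Reason: Adverse Event/Side Effects/Complication" and, as a separate entry, "Patient withdrawal or refusal after" the start of protocol therapy, along with physician decision and other reasons.

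**The concern.** There are two mismatches.

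The first is in the event. The wording of 5.2.1 is loose, but it requires intolerance; 11.2.1 drops that requirement. A patient who stops the regimen for a reason unrelated to the product is a non-event under 5.2.1 and a tolerability failure under 11.2.1. Nothing says which section governs, so the definition could be chosen after the data are seen.

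The second is between objective and analysis. A comparative objective has only separate per-arm intervals, so the comparison would be read by eye from two wide intervals. Sections 11.2.2 to 11.2.4 all name a between-group comparison for their endpoints; 11.2.1 does not. The primary analysis in 11.1 is also per arm, but its objective is not comparative: "To determine the feasibility of the use of KeraStat Cream in patients receiving radiotherapy for head and neck cancer".

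The Study Rationale in Section 1.0 says that tolerability must be confirmed first and that these data will inform later randomised comparative trials. A tolerability rate whose meaning depends on the section consulted is a poor input to them.

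**Working it through.** **The plan's own precision figure.** Section 11.3 gives a maximum total interval width of 0.578 for compliance with 12 per arm. The exact (Clopper-Pearson) 95% interval for 6/12 is 0.2109 to 0.7891, width 0.578, so the figure reproduces. The exact method is used below for single proportions. The plan gives no precision figure for tolerability.

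**Inputs.** Section 11.3 has 28 enrolled with equal allocation, so 28/2 = 14 per arm. The documents give no discontinuation rate. Assumptions for illustration: no true intolerance in either arm, and 0 to 4 unrelated regimen stops in total. The upper end borrows the plan's allowance of 28 - 24 = 4 non-completers; leaving the study is not the same event as stopping the regimen.

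**Per-arm tolerability (exact 95% CI).**

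| Unrelated stops in the arm | Under 5.2.1 | Under 11.2.1 |
|---|---|---|
| 0 | 14/14 = 100% (76.8 to 100) | 14/14 = 100% (76.8 to 100) |
| 1 | 14/14 = 100% (76.8 to 100) | 13/14 = 92.9% (66.1 to 99.8) |
| 2 | 14/14 = 100% (76.8 to 100) | 12/14 = 85.7% (57.2 to 98.2) |
| 3 | 14/14 = 100% (76.8 to 100) | 11/14 = 78.6% (49.2 to 95.3) |

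Each unrelated stop moves the 11.2.1 estimate by 1/14 = 7.1 points and leaves the 5.2.1 estimate unchanged.

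**Between-arm difference (Newcombe 95% CI).** With Wilson limits (l, u) for each arm and d = p1 - p2:

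- lower limit = d - sqrt[(p1 - l1)^2 + (u2 - p2)^2]
- upper limit = d + sqrt[(u1 - p1)^2 + (p2 - l2)^2]

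For 13/14 against 11/14, the Wilson limits are 0.685 to 0.987 and 0.524 to 0.924, and d = 0.929 - 0.786 = 0.143.

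- lower = 0.143 - sqrt(0.243^2 + 0.139^2) = 0.143 - 0.280 = -0.137
- upper = 0.143 + sqrt(0.059^2 + 0.262^2) = 0.143 + 0.268 = 0.411

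| Case | Difference (95% CI), points |
|---|---|
| 5.2.1, however the stops split: 14/14 vs 14/14 | 0 (-21.5 to 21.5) |
| 11.2.1, two stops split 1-1: 13/14 vs 13/14 | 0 (-25.0 to 25.0) |
| 11.2.1, four stops split 2-2: 12/14 vs 12/14 | 0 (-27.6 to 27.6) |
| 11.2.1, four stops split 3-1: 13/14 vs 11/14 | 14.3 (-13.7 to 41.1) |

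**How often four stops split unevenly by chance.** There are C(28,4) = 20,475 ways to choose the four patients.

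- 2-2: 91 x 91 / 20,475 = 40.4%
- 3-1 either way: 2 x 364 x 14 / 20,475 = 49.8%
- 4-0 either way: 2 x 1,001 / 20,475 = 9.8%

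An uneven split therefore occurs 59.6% of the time.

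**The case against.** **One loosely drafted endpoint.** Both sections contain the phrase about any reason. Section 6.4 names only intolerance and agent-related adverse events as grounds for discontinuing the study cream, and 6.6 deals separately with leaving the study. The authors may have meant one thing throughout. But reading both as all-cause leaves the intolerance condition in 5.2.1 without function, and 6.4 does not narrow what 11.2.1 counts. The literal conflict remains.

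**The illustration is constructed.** This stands. The counts are assumed, and any four events, including four genuine intolerance stops, would split unevenly just as often. The probabilities describe small-sample noise. What belongs to 11.2.1 is that noise from unrelated stops carries a tolerability label. The 14.3-point interval includes zero.

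**All-cause discontinuation has merits.** It needs no judgement of cause in an open-label trial, and an intolerance-only count treats patients who stopped for other reasons as tolerant although their later tolerance is unobserved. This stands, and is why both measures should be reported.

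**The contrast may not be like for like.** Routine care allows several products, so a patient there may switch where a KeraStat patient would stop, and the plan does not say whether a switch counts. This stands as a limit on any between-arm reading. Stops truly unrelated to either regimen should not bias the contrast on average; stops influenced by knowledge of the assignment could.

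**The Off Treatment Form is generic.** It carries entries irrelevant to this trial and is not in the study calendar or the data management table. Appendix G is in both and is the better main source.

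**Per-arm intervals are a defensible pilot choice.** They are, but the objective would then need descriptive wording.

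**Conclusion.** The concern holds on both limbs. Sections 5.2.1 and 11.2.1 define different events, and no other section settles which applies. Objective 2.2.1 is comparative and its analysis is not.

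The text establishes the conflict without any assumption. Its numerical size rests on 14 per arm and assumed stops. The sample size, the 0.578 figure and the primary analysis are unaffected, and no loss of power is claimed. It should be fixed, in proportion to a secondary pilot endpoint: the damage is to how tolerability is reported and carried forward.

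**What to change.** Reconcile 5.2.1 and 11.2.1 by reporting two measures in each arm among all randomised patients:

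- **(a) Tolerability:** discontinuation of the assigned regimen because of intolerance. Judge it by one written rule, the same in both arms, from the reason on Appendix G, supplemented by the Off Treatment Form and CRF.
- **(b) Any-reason discontinuation:** labelled as that, not as intolerance.

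For each, keep the planned per-arm 95% CI and add the between-arm difference in proportions with a 95% CI (Newcombe, for example), as estimation without a powered test. State that patients who leave the study are classified by their recorded reason, and whether a product switch within routine care counts as discontinuation. Do not define (a) by the causality rating in 8.1.4: it is made against the study device and has no like-for-like counterpart under routine care. If the sponsor wants no contrast, rewording 2.2.1 as descriptive by arm would resolve the second mismatch only.

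The cost is wording and one added estimate, with no new form, visit or patients. Section 7.1.3 does not list Appendix G for the early-termination visit, so for some leavers the Off Treatment Form or CRF may be the only source. Reasons must be classified in an open-label trial, which (b) offsets. The between-arm interval will be wide: about +/-22 to +/-28 points at 14 per arm when the arms are equal with 0 to 2 stops each.
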